Hypotheses. The primary hypothesis is that survival without neurodevelopmental impairment (NDI) at 18-22 months adjusted age will be greater with initial laparotomy rather than with initial drainage.

Methods. Inclusion criteria are 1) birth weight of $\leq 1,000$ g, 2) a decision to perform surgery for suspected NEC or IP, 3) the infant is less than or equal to 8 weeks of age (8 0/7 weeks or less) at the time of eligibility assessment, and 4) patient is at a center able to perform both laparotomy and drainage. Exclusion criteria are: 1) major anomaly which influences likelihood of developing primary outcome or affects surgical treatment considerations; 2) congenital infection; 3) prior NEC or IP; 4) prior laparotomy or peritoneal drain placement; and 5) follow-up unlikely and 6) infant for whom full support is not provided (including surgical treatment). To facilitate enrollment, the trial will be discussed with the parents of potentially eligible infants when NEC or IP is first suspected. Consent will be diligently sought for randomization utilizing members of the multidisciplinary research team (i.e. research coordinator, neonatologist, pediatric surgeon). For infants that are not randomized (due to refusal of consent or unwillingness of the neonatologist and/or surgeon to enroll the infant), consent will be sought to enroll the infant into the study as a member of the "preference cohort". These infants will be treated according to the preference of the surgeon and neonatologist and will have similar data collection as for randomized infants. **Enrollment in the preference cohort was terminated on February 14, 2013.** Infants will be enrolled by calling RTI International as soon as a decision to perform surgery is made (or via a computer randomization process). Randomized infants will be stratified according to two variables: center and according to the overall risk for death or NDI (higher / lower). The risk stratification formula was primarily developed in the prospective observational model and includes the following variables: birth-weight, gestational age, vasopressor requirement (yes / no), if infant is on high frequency (oscillating or jet) ventilation or not (any modality of conventional ventilation or no mechanical ventilation), pH, FiO₂, and preoperative diagnosis (NEC or IP). Treatment beyond the initial surgical management will be unaffected by the trial. Data collection (beyond that for the generic data base) will be limited, and the forms will be based on those used in the observational study. Outcome at 18-22 months will be assessed by evaluators who are masked to the details of the operative intervention(s) that have been performed using standard Network assessments.

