We are proposing to conduct this trial purely within the Network as long as adequate enrollment can be achieved. If enrollment is below the predicted rate that would allow completion of the trial in 4 years, we would propose to add additional sites as needed to allow adequate enrollment. Both randomized trials published in this area have been halted prior to achieving the desired sample size. It would be unwise to ignore this history. Thus, we propose to critically evaluate actual versus desired enrollment at 6 months and carefully consider the need / desirability of recruiting additional sites.

Comprehensive cohort design. This design differs from that of a conventional randomized trial by including not only patients whose treatment is randomly assigned but also any whose treatment is based on the preference of the physician or patient (or surrogate). When properly performed, every effort is made in these trials to promote clinical equipoise and obtain informed consent to be randomized. If such consent is refused, consent is sought only for data collection. Whenever possible, the determination of primary outcome is carefully standardized and assessed by masked evaluators. Baseline data are carefully collected and controlled during analysis to adjust for baseline differences between patients who receive different therapies.

This approach has the potential advantage of increasing the number of patients studied and the external validity (generalizability) of the results by involving patients and physicians who otherwise would not be involved.¹⁰ However, an increase in external validity would be important only if the internal validity of the results is not undermined. Based on surveys of purely observational studies, one would expect that inclusion of preference groups would bias the results. This problem might be avoided or minimized because of measures to promote equipoise prior to the study, stringent features of study design and analysis as noted above,

exclusion of centers with such strong biases that they are unwilling to randomize any patients, and the balancing of biases within and between centers that do participate. A systematic review published in JAMA this year¹⁰ assessed all trials using a comprehensive cohort design. The review concluded that “Differences in outcome between randomized and preference groups were generally small, particularly in large trials and after accounting for baseline measures of risk”.

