- parenteral nutrition associated cholestasis, (**variable name is Patient.PN_assoc_chol**)
- length of hospital stay, (**variable name is Patient.GDB_HOSPSTAY**)
- rehospitalizations, (**variable name is Patient.?**)
- each component of the primary outcome;
 - Cerebral Palsy classification (GMFCS Level ≥ 2) [**classification variables are Patient.GMFCS_GTE2 and Patient.Any_CP, while the raw variable for GMFCS is Patient.EFGROSS.**]
 - BSID III score (Bayley III Cognitive score < 85) [**classification variable is Patient.LowBayley, while the raw variable is Patient.NF9ABSCC.**]
 - Vision assessment (< 20 - 200 vision or legally blind) [**classification variable is Patient.BILATERAL_BLINDNESS, while the raw variables are Patient.EFVISNL and Patient.EFVISNR.**]
 - Hearing assessment (permanent hearing loss) [**classification variable is Patient.DEAF, while the raw variable is Patient.EFHEARIM.**]

Study Methods

Overall Study Design and Plan

Similar to a Comprehensive Cohort Design, the study design is an unmasked randomized trial accompanied by a nonrandomized cohort. Data from the nonrandomized cohort will be analyzed and results compared to similar results derived from analyses of randomized cohort data. Covariate adjustment methods, and propensity scores will be utilized in an attempt to adjust for selection bias in the nonrandomized cohort. The nonrandomized cohort is not a representative sample of all eligible infants not randomized, but it is a sample of eligible infants whose surgeon, neonatologist, or parents refused randomization. If the results from properly adjusted analyses of nonrandomized cohort data are similar to the results from the analyses of randomized cohort data, then we have some evidence for the generalizability of the randomized cohort results. On the other hand, if important differences do occur, then differences will need to be explained using reasonable arguments not grounded in statistical theory but clinical understanding. Enrollment into the nonrandomized cohort was terminated on February 14, 2013.

Selection of Study Population

Inclusion Criteria:

1. birth weight of $\leq 1,000$ g,
2. a decision by the attending pediatric surgeon to perform surgery for suspected NEC or IP (The indications for surgery for infants with NEC or IP vary among surgeons and sites),
3. the infant is less than or equal to 8 weeks of age (8 0/7 weeks or less) at the time of eligibility assessment, and

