- 2) If a propensity model can be built using covariates that are understood to be related to the treatment selection process and the model produces propensity scores which balance baseline covariate distributions among the groups, then the primary outcome will be analyzed using a robust Poisson regression model that will include propensity score logits as a covariate.
- 3) If the robust Poisson regression model is fit in step 4, then the estimated risk and propensity score adjusted relative risk will be compared to the risk adjusted relative risk calculated using the randomized subject data.
- 4) An informal comparison of relative risk point estimates and confidence intervals will be used to assess the similarity of the two relative risk estimates.

Combined Analysis of Randomized and non-Randomized Cohorts

This work is solely exploratory and will only be completed if analysis of non-Randomized Cohort can be considered useful. If the risk adjusted relative risk estimates in the two cohorts are in the same direction, or the propensity adjusted relative risk among the non-randomized cohort is in the same direction as the risk adjusted relative risk estimate in the randomized cohort, then a random-effects meta-analysis will be used to estimate the overall relative risk. The following will be done to complete this meta-analysis:

- 1) Estimate the overall treatment effect on the log RR scale using a fixed effect model:

$$\log(RR)_F = \frac{\sum w_i [\log(RR)_i]}{\sum w_i},$$

where $w_i = 1 / v_i$ and v_i is the variance of the i^{th} estimate of $\log(RR)$.

2) Estimate the Q statistic, which can be used to test for heterogeneity of treatment effect:

$$Q = \sum w_i [\log(RR)_i - \log(RR)_F]^2.$$

3) Estimate the variance needed for a random effects model:

$$\sigma^2 = \max \left\{ 0, \frac{Q - (2 - 1)}{\sum w_i - (\sum w_i^2) / \sum w_i} \right\}.$$

4) Estimate the random effect weights:

$$\tilde{w}_i = \frac{1}{\sigma^2 + v_i}.$$

5) Estimate the overall random effect estimate of log(RR):

$$\log(RR)_R = \frac{\sum \tilde{w}_i [\log(RR)_i]}{\sum \tilde{w}_i}.$$

6) Estimate a 95% CI for the random effect estimate of the log(RR):

$$\log(RR)_R \pm \frac{1.96}{\sqrt{\sum \tilde{w}_i}}.$$

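### The preference cohort closed on February 14, 2013, but its relative risk is compared, and may be pooled, with that of all randomized infants whatever their enrollment date

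*SAP*

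**What the plan says.** Both documents give the same closure date. The SAP (Overall Study Design and Plan) states: "Enrollment into the nonrandomized cohort was terminated on February 14, 2013". The protocol abstract (Methods) states: "Enrollment in the preference cohort was terminated on February 14, 2013". Neither describes randomization as closed.

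Under Propensity Analysis of Primary Outcome using non-Randomized Cohort Data, the SAP says that the adjusted RR from the nonrandomized infants "will be compared to the risk adjusted relative risk calculated using the randomized subject data". The method is loose: "An informal comparison of relative risk point estimates and confidence intervals will be used to assess the similarity of the two relative risk estimates". If the cohorts point in the same direction, the next section, Combined Analysis of Randomized and non-Randomized Cohorts, adds: "then a random-effects meta-analysis will be used to estimate the overall relative risk". That pooling is qualified: "This work is solely exploratory and will only be completed if analysis of non-Randomized Cohort can be considered useful".

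The intended reading is in Overall Study Design and Plan: if properly adjusted results are similar, "then we have some evidence for the generalizability of the randomized cohort results". The same paragraph concedes that the nonrandomized infants do not represent all eligible infants who were not randomized. It does not mention calendar period.

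**The concern.** Secondary Specific Aim 1 and Secondary Hypothesis 1 rest on this comparison. It is meant to vary one thing, namely whether treatment was assigned by randomization or by preference. If randomization outlasted the preference cohort, the comparison also varies enrollment period, because infants randomized after February 14, 2013 have no preference counterparts.

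The planned adjustments do not deal with this. The propensity score models the choice of laparotomy or drain inside the nonrandomized cohort. Its 25 to 50 baseline measures are not listed and could include date or center, but that would balance laparotomy and drain infants within that cohort, not align the enrollment periods of the two cohorts. The randomized model has main effects for treatment, risk stratum and, if possible, center. It has no term for period.

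At stake is how a secondary result is read. The protocol (Comprehensive cohort design) would presume generalizability if both cohorts favor the same therapy. Because the comparison is informal, like-for-like inputs are its main safeguard.

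**Working it through.** **1. The plan's own figures.** Protocol, Sample Size: 160 eligible per year × 50% consent × 4 years = 320 randomized. Then 160 deaths + 0.90 × 160 survivors = 304 with an outcome. For 80% versus 65% at 150 per arm, exact enumeration of the two-sided Fisher test gives power 0.803. The plan's figures reproduce.

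**2. Did randomization continue after closure?** This is inferred.
- The SAP was first dated August 1, 2013, 168 days after closure. It still describes randomization as future and schedules efficacy looks at about 75, 150, 225 and 300 randomized infants.
- The protocol date is September 8, 2009. Four planned years from then end in September 2013, and the five-year limit in September 2014.
- Only the nonrandomized cohort is said to have closed.

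**3. Share randomized after closure (assumed start dates and rates).** Randomized by closure = rate × years from start to February 14, 2013. The rates are the planned 80 per year (320 in 4 years) and 60 per year (300 in 5 years).

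| Assumed start | Rate per year | By closure | After closure |
|---|---|---|---|
| Sep 8, 2009 (3.44 years) | 80 | 275 of 320 | 45 (14%) |
| Sep 8, 2009 | 60 | 206 of 300 | 94 (31%) |
| Jul 1, 2010 (2.63 years) | 80 | 210 of 320 | 110 (34%) |
| Jul 1, 2010 | 60 | 158 of 300 | 142 (47%) |
| Jan 1, 2011 (2.12 years) | 80 | 170 of 320 | 150 (47%) |
| Jan 1, 2011 | 60 | 127 of 300 | 173 (58%) |

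**4. When the mismatch matters.** Each RR is a contrast within its own cohort. With a constant RR, period creates no gap. Suppose instead (assumption) that the true RR is 0.65/0.80 = 0.8125 before closure and 1.0 after, with drain risk 0.80 throughout. With fraction f randomized before closure, the all-randomized RR is [0.65f + 0.80(1 − f)]/0.80.
- f = 0.86: 0.671/0.80 = 0.839, a factor of 1.03 from 0.8125.
- f = 0.69: 0.6965/0.80 = 0.871, a factor of 1.07.
- f = 0.42: 0.737/0.80 = 0.921, a factor of 1.13.

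Case mix alone can also move an RR at such high event rates. The planned risks give an odds ratio of (0.65/0.35)/(0.80/0.20) = 0.464. If that odds ratio is held fixed (assumption), a drain risk of 70% gives a laparotomy risk of 52% and RR 0.74; a drain risk of 90% gives 80.7% and RR 0.90.

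**5. What restriction costs.** With n per arm and the planned risks, SE(log RR) = √[0.20/(0.80n) + 0.35/(0.65n)].

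| Randomized infants | SE(log RR) | 95% CI factor |
|---|---|---|
| 300 | 0.073 | 1.15 |
| 200 | 0.089 | 1.19 |
| 150 | 0.103 | 1.22 |

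The comparison also carries the nonrandomized cohort's error, and that cohort's size is not given. Assume 150 infants, evenly split, with the same risks (SE 0.1025). The SE of the difference is √(0.0725² + 0.1025²) = 0.126 against 300 randomized (factor 1.28) and √(0.0888² + 0.1025²) = 0.136 against 200 (factor 1.30).

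**The case against.** The other side has real force.

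- **A period shift is not in itself bias.** A change in baseline risk over time does not confound either within-cohort contrast. The comparison is distorted only if the RR varies with period, and no document shows that it does. This stands, and the point is conditional for that reason.
- **The plan already hedges.** The protocol says a difference could arise from chance, true differences in effectiveness, residual confounding or other causes. The SAP calls the comparison informal and the pooling exploratory. This limits the weight of the point. But period is not named among the explanations, and the hedges deal mainly with disagreement. Agreement is read as support.
- **The comparison is imprecise anyway.** The assumed shift above yields a gap of 1.03 to 1.13, inside a 95% factor of about 1.28. The data could not tell such a gap from chance. That argues against strong claims, not against showing the concurrent figure.
- **The aim concerns the trial's result.** Secondary Aim 1 asks whether nonrandomized data support the RR among randomized infants. Replacing the full randomized cohort as lead comparator would change that target. This stands, so the concurrent version belongs beside the planned one.

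Two stronger readings are tempting. A reader might infer that cohort is also confounded with site, since the protocol (Critical Design Issues) says that if enrollment is low, "we would propose to add additional sites as needed to allow adequate enrollment". That is a contingency, tied to a review at about 6 months. Neither document says that a site was added, or when. A reader might also take the range of later laparotomy after a drain, 9% to 74% in the studies the protocol reviews, as evidence of drift. Those figures come from separate studies with different rules; they show variation between studies and are not a time trend.

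**Conclusion.** The point holds in limited form. The comparison and the possible pooling use randomized infants without regard to enrollment date, although the nonrandomized cohort has a fixed closing date. If the RR changed with period through case mix, practice or possibly site mix, the planned comparison cannot separate that from preference status. If the RR was constant, or if randomization in fact ended by the same date, nothing is lost.

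The effect size cannot be derived from the documents. The 14% to 58% enrolled after closure, and the gap factors of 1.03 to 1.13, rest on assumed start dates, accrual rates and an assumed RR shift. The documents do not support a claim that the result is biased, that site confounding is established, or that the primary analysis is affected. This is a minor, inexpensive improvement to a secondary, informal aim.

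**What to change.** In the SAP sections on the propensity analysis and the combined analysis:

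1. Report the first and last randomization dates, and the number randomized by arm on or before February 14, 2013 and after it.
2. Keep the planned comparison with all randomized infants. Beside it, show the same model restricted to infants randomized on or before that date.
3. If pooling is done, add a pooled estimate using the restricted randomized RR.
4. Optionally, add a further row limited to centers that contributed to both cohorts.
5. Name enrollment period among the possible explanations for a difference or an agreement.

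The work is a date filter on data already held and one extra row per table. The cutoff is fixed by the documents, so it leaves the analyst no choice to make. The cost is the wider interval for the concurrent estimate shown in the working. The primary analysis of the randomized cohort stays as it is.

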the Bayley tests. We plan to critically examine these data (GDB data, pooled data from NEST study subjects, and publicized data from other studies) at yearly intervals during the trial enrollment period. The sample size determination will be reevaluated, and may be revised upwards as the uncertainty regarding the Bayley III lessens (2 years after study commencement). These decisions will be made by the Steering Committee based upon a recommendation by the NEST subcommittee, and without any knowledge of the difference between the two treatment groups in this trial with regard to the proportion of impaired children.

Sample Size. Allowing for a smaller difference between treatment groups in the trial than in our observational study, we hypothesize that 80% of the drain group and 65% of the laparotomy group will die or be impaired at 18-22 mo. (Number needed to treat = only 7 to gain one unimpaired survivor from laparotomy). By PASS software, a total sample size of 300 infants who have their outcome assessed is needed with $\alpha = 0.05$ and $\beta = 0.20$ using 2-sided Fisher exact test.

In the observational study 156 infants were enrolled in 14 centers in 18 months. By extrapolating these numbers to a 16-center trial design, 120 eligible patients / year would be expected. Based on the latest GDB data, using the 16 centers prior to reformatting the Network, an estimated number of eligible babies of 190 is obtained. Our best estimate of the number of eligible patients in the new 16-center Network is 160 / year. We anticipate a 50% enrollment rate, $\geq 95\%$ consent for data collection (as for generic data collection), equal use of initial laparotomy and drains; and a 50% mortality in each group. Assuming a consent rate of 50%, 320 patients would be enrolled in a 4-year period with 160 deaths and 160 survivors. With a 90% follow up rate, 144 survivors would have the primary outcome measured. This would yield 304 patients which will meet our sample size requirement during a 4-year enrollment period. If the consent rate is below 50%, the enrollment period would need to be extended.

We propose that the trial be stopped when any of the following are met: 1) DSMC might stop trial for large difference in neonatal mortality (secondary outcome), which is unlikely given equivalent survival in both observational study and two randomized trials; 2) 300 randomized patients are enrolled and have primary outcome assessed; or 3) a 5-year enrollment period has elapsed.

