Estimates of baseline risk adjusted relative risk on the log scale and the standard errors will be estimated from the robust Poisson regression models. The variance for the estimated baseline risk adjusted relative risk on the log scale will equal the square of the standard error calculated from the sandwich estimator.

Statistical Appendix A: Exploratory Analysis for Statistician's benefit (will be completed only after all publication required analyses are completed.)

Interestingly, bootstrap analysis of a binary outcome using Poisson regression, when the outcome is a function of treatment, produces an empirical distribution of estimated relative risk on the log scale that is approximated by a normal distribution. Also, an empirical 95% confidence interval for the relative risk on the log scale calculated from these bootstrap samples will approximate a 95% confidence interval for the relative risk on the log scale calculated for a robust Poisson regression model.

For example, using simulated data containing a binary outcome which is a function of treatment and a two level strata variable, the following results occurred:

- The estimated $\log(\text{RR})$ using a robust Poisson regression model was -0.209, compared to the true value of -0.208.
- The 95% CI for the treatment effect on the $\log(\text{RR})$ scale using robust Poisson regression was -0.347 to -0.071.
- The estimated median bootstrap estimate of $\log(\text{RR})$ using Poisson regression was -0.209, based on 10000 bootstrap samples.
- The 95% CI for the treatment effect on the $\log(\text{RR})$ scale using the bootstrap estimates was -0.356 to -0.078.

Also, Figure 1 shows that the 10,000 bootstrap estimates of $\log(\text{RR})$ from the Poisson regression does approximate a normal distribution.

[figure not shown]

Figure 1

The program used to study the relation between robust Poisson regression and bootstrapped Poisson regression of a binary outcome is included in Statistical Appendix B.

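### The pooled interval for the two cohorts is labelled 95%, but it treats a between-cohort variance estimated from two cohorts as known, so its coverage of the random-effects mean can fall well below 95%

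*SAP*

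**What the plan says.** The SAP section Combined Analysis of Randomized and non-Randomized Cohorts opens with a limit: "This work is solely exploratory and will only be completed if analysis of non-Randomized Cohort can be considered useful". It then sets a trigger, "If the risk adjusted relative risk estimates in the two cohorts are in the same direction" (or if the propensity-adjusted estimate agrees with the randomized one), and adds "then a random-effects meta-analysis will be used to estimate the overall relative risk".

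Six steps follow:
- Steps 1 and 2 compute the inverse-variance average and Q.
- Step 3 estimates the between-cohort variance by moments, using Q minus (2 − 1), and truncates it at zero.
- Steps 4 and 5 reweight by 1/(σ² + v_i).
- Step 6 reads "Estimate a 95% CI for the random effect estimate of the log(RR" and closes the bracket; the interval is the estimate ± 1.96/√(sum of the new weights).

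On the within-cohort variances the SAP says: "The variance for the estimated baseline risk adjusted relative risk on the log scale will equal the square of the standard error" from the sandwich estimator. It gives no small-sample correction and no prior for the between-cohort variance. It does not define the overall relative risk further, and neither document gives the preference cohort's size or an expected between-cohort SD.

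Agreement between the cohorts is to be judged by an informal comparison of relative risks and confidence intervals (SAP, Propensity Analysis, last step). The protocol (Statistical Analyses) says the combined work will not affect the primary analysis of the randomized cohort.

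**The concern.** A multiplier of 1.96 gives 95% coverage when the between-cohort variance is known. Here it is estimated on one degree of freedom and is often zero when the true value is not. The interval then collapses to the fixed-effect one, in just the heterogeneous case that a random-effects model is meant to cover.

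The weights raise a second issue. Random-effects weights move toward equality as the cohorts disagree, so a preference cohort that is the smaller one gains influence. The protocol (Comprehensive cohort design) names residual confounding as the most likely reason for a difference if, as in prior studies, non-randomized infants treated with drains are at systematically higher risk.

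At stake is how the pooled result is read. Gaining experience with comprehensive cohort methods is a stated trial objective, and an interval whose label is wrong under its own model weakens that lesson.

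**Working it through.** **Inputs from the documents.** The protocol's Sample Size section says "we hypothesize that 80% of the drain group and 65% of the laparotomy group will die or be impaired at 18-22 mo" and "a total sample size of 300 infants who have their outcome assessed is needed", that is, 150 per arm. Exact enumeration of the two-sided Fisher test at 150 per arm gives power 0.803, so the stated 80% is reproduced.

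**Within-cohort variance.** For the randomized cohort, v₁ = (1 − 0.80)/(150 × 0.80) + (1 − 0.65)/(150 × 0.65) = 0.00167 + 0.00359 = 0.00526, so SE = 0.0725. The simulated example in SAP Appendix A implies (0.347 − 0.071)/(2 × 1.96) = 0.0704, which agrees closely.

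**Assumptions.** The preference cohort has 100, 200 or 300 infants at the same rates, so v₂ = 0.0158, 0.0079 or 0.00526. The true between-cohort SD of log RR (τ) runs from 0 to 0.20. For scale, the planned effect is log(0.8125) = −0.208, so τ = 0.20 is about as large as the whole treatment effect.

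**What steps 3 to 6 reduce to.** With two cohorts and d the difference in log RR, Q = d²/(v₁ + v₂) and σ² = max{0, [d² − (v₁ + v₂)]/2}. The estimate is zero whenever Q ≤ 1, which has probability P(|Z| < √[(v₁ + v₂)/(v₁ + v₂ + 2τ²)]):
- τ = 0.10, 100 infants: √(0.0210/0.0410) = 0.716, probability 53%.
- τ = 0.20, 300 infants: √(0.0105/0.0905) = 0.341, probability 27%.

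**Coverage of the random-effects mean.** Steps 1 to 6 were simulated as written, without the same-direction trigger:

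| True SD of log RR | 100 infants | 200 infants | 300 infants |
|---|---|---|---|
| 0 | 96% | 96% | 96% |
| 0.05 | 93% | 93% | 93% |
| 0.10 | 87% | 86% | 85% |
| 0.15 | 81% | 81% | 80% |
| 0.20 | 78% | 77% | 76% |

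**Check on the limit.** For equal variances and σ² > 0, the interval is the midpoint ± 0.98|d|. When τ dominates, the midpoint's error divided by |d|/2 follows t on 1 df, so coverage tends to P(|t₁| < 1.96) = (2/π) arctan(1.96) = 70%. The matching multiplier would be 12.706.

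**Effect of the trigger.** Restricted to same-direction pairs with 100 to 150 infants, coverage at τ = 0.10 to 0.20 is 88% to 76% if the mean RR is 0.8125, and about 73% to 55% if it is 1. The trigger gives no protection.

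**Weight shift.** Take 100 preference infants, randomized RR 0.8125 and preference RR 0.60:
- d = −0.303, and Q = 0.0919/0.0210 = 4.37.
- σ² = (0.0919 − 0.0210)/2 = 0.0354.
- The preference weight moves from 0.00526/0.0210 = 0.25 to (0.00526 + 0.0354)/0.0919 = 0.44.
- The pooled RR moves from 0.75 to 0.71, and the random-effects interval is 0.53 to 0.95.
- The fixed-effect interval is narrower: 0.753 × exp(± 1.96 × 0.0628) = 0.67 to 0.85.
- At preference RR 0.70, Q is 1.06 and the weight is only 0.26. The shift needs Q > 1, cannot pass one half, and is absent with equal cohorts.

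**Other targets, τ = 0.10 to 0.20:**

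| Target | SAP interval | Fixed-effect interval |
|---|---|---|
| Random-effects mean | 87% to 76% | 78% to 49% |
| Precision-weighted average of these two cohorts | 97-98% | 95% |
| Randomized cohort's own effect | 91-96% | 91% to 50% |

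**The case against.** The strongest reply is that the shortfall belongs to one target. The SAP says only overall relative risk and describes no population of cohorts. If the two cohorts differ by a fixed amount, which is how a systematic bias in the preference cohort would act, the interval covers the midpoint of the two effects 91-100% of the time over the settings examined. It also over-covers the precision-weighted average. This stands, and it is why the coverage figures must be tied to the random-effects mean and to a stated SD. It does not rescue the label: the SAP chose a random-effects model and attached 95% to the interval that model yields.

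A reader might infer that coverage is poor whenever the cohorts differ. The documents do not support that: at SD 0.05 the loss is about 2 points, and no SD is given.

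A reader might also infer that dropping steps 3 to 6 for the fixed-effect interval would cure the problem. It would not. That interval is never wider, and it covers the same mean only 49-78% of the time at SD 0.10 to 0.20. Suppose a preference cohort of 100 is biased by −0.28 on log RR (both assumed). The mean preference weight rises from 25% to 40%, yet the SAP interval covers the randomized effect 94.5% of the time against 80% for the fixed-effect one. The weight shift is a known property of random effects and comes with a wider interval.

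Finally, the work is exploratory and no decision rule uses it. That limits the importance of the point but does not answer it.

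**Conclusion.** The point holds in a limited form. Under the random-effects model the SAP adopts, the step 6 interval is not a 95% interval for the mean effect unless between-cohort variation is very small. Coverage is about 96% at SD 0, 93% at 0.05, 85-87% at 0.10 and 76-78% at 0.20, tending to 70% for larger SDs. These figures rest on 300 randomized infants at the planned rates, an assumed 100 to 300 preference infants, normal log RRs, and exchangeable cohort effects.

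The weight shift is real only if the preference cohort is the smaller one. Enrollment into it closed on February 14, 2013, which makes that plausible, but the documents do not state its size.

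Nothing here bears on the primary result, and nothing shows that a fixed-effect analysis would be better. This is a minor, inexpensive correction.

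**What to change.** 1. Do not call the step 6 interval a 95% CI for the overall RR.
2. If a random-effects summary is kept, fit it in the WinBUGS/JAGS set-up already planned, with a pre-specified, weakly informative prior on the between-cohort SD, so that its uncertainty reaches the interval. One example is a half-normal with scale 0.2 on log RR, plus a second scale as a sensitivity analysis. In simulation with scale 0.2, coverage of the mean was 94% or higher in every setting above.
3. In all cases report each cohort's RR, and the ratio of the two RRs with its 95% CI, exp(d ± 1.96√(v₁ + v₂)), as the measure of agreement in place of the informal comparison alone. In the worked example the ratio is 0.60/0.8125 = 0.74, with interval exp(−0.303 ± 1.96 × 0.145) = 0.56 to 0.98.
4. The step 1 estimate may be shown if labelled the precision-weighted average of these two cohorts. It must not be presented as a better-covering replacement.

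A Hartung-Knapp interval on 1 df restores coverage to 93-95%. At SD 0.10 to 0.20 with 100 to 150 preference infants, however, its upper limit is about 4.5 to 14 times its lower limit on the RR scale, so it says little.

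The cost is a change of SAP wording and one small model. The downsides are a wider pooled interval that is conservative when the cohorts truly agree, and dependence on the stated prior: a scale set too small brings the shortfall back, hence the sensitivity scale.
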